### **Significance**

#### **Scope of the Problem**

The number of Americans 65 years and older will double in size over the next 40 years. Aging brings increased cognitive decline. Alzheimer's disease (AD), the most common type of dementia, is of particular concern to the health care system, with an expected two-fold increase in prevalence over the next 30 years and high direct and indirect costs of care. We must find effective interventions to reduce the burden of AD on our society and economy. Much like the field of heart disease 30 years ago, reducing AD prevalence through primary prevention is now the focus of broad research investment. There is evidence that risk of cognitive decline can be moderated by lifestyle interventions such as physical exercise, although the extent literature is not conclusive. Conflicting evidence is likely a result of imprecisely controlled interventions and a lack of understanding about key target mechanisms. There are several potential mechanisms that may relate exercise with brain health. Our aims are designed to specifically explore cerebral blood flow (CBF) as a potential mechanism of exercise effects on brain and cognition, and is specifically related to the APOE allele, the strongest genetic risk factor for late-onset AD.. Understanding how exercise promotes cognition and brain health is essential to fully capitalize on its benefits for the treatment and prevention of AD.

#### **Exercise Represents a Promising Strategy for Reducing Risk of Cognitive Decline**

Exercise --defined as planned, repetitive physical activity-- has a biologically plausible and temporal relationship with heart disease, atherosclerosis, stroke, diabetes, obesity, hypertension, depression, all established risk factors for dementia. Aerobic exercise is among the most important and cost effective tools available for chronic disease management. Our work along with others' strongly suggests that moderate-intensity aerobic exercise benefits brain health and cognition.

**Exercise, Cognition and Brain Health:** Longitudinal studies suggest physical activity is positively associated with cognition and brain health and reduced risk of cognitive decline and dementia. Perhaps more compelling, RCTs have repeatedly demonstrated benefits of aerobic exercise on cognition (particularly in executive and visuospatial function) and measures of brain health such as whole brain and hippocampal volume in people with and without cognitive decline.

#### **Cerebrovascular Health is Vital for Cognitive Function and Brain Health**

The brain is intolerant of ischemia and highly dependent on healthy blood supply, requiring up to 25% of whole body resting O2 consumption. Consequently, CBF is highly regulated to protect against hypoperfusion. There is increasing evidence that cerebrovascular dysfunction contributes to AD. In animal models,  $\beta$ -amyloid disrupts cerebrovascular regulation. In humans, morphological changes occur in cerebral arteries in AD. Additionally, CBF is lower in people with neurodegenerative diseases such as AD, and cerebrovascular pathology precedes and accompanies neurodegeneration. Reasons for lower cerebral blood flow are unclear but may include diminished heart function, atherosclerosis risk, and deficits in vessel wall health.

Our previous work suggests the presence of  $\beta$ -amyloid, in otherwise cognitively intact individuals, is associated with altered cerebrovascular regulation measured at rest and during exercise (see Figure 1). Further investigation of CBF regulation is therefore vital to understanding cognitive decline and the development of AD.

**Aerobic exercise effects on CBF may only become apparent when dynamically measured during exertion.** Measuring CBF following exercise rather than at rest may provide a more sensitive and relevant measure for detecting differences in subjects at risk for AD.

**Cerebral Blood Flow Improves with Exercise:** There is considerable interest in precisely defining cerebrovascular adaptations to aerobic exercise and how those adaptations may support cognitive function. We know that sedentary older adults demonstrate decreasing CBF over time. Habitual exercise appears to increase CBF, and older athletes who take time off of training quickly experience reductions in CBF. Additionally, heart disease and stroke patients improve CBF while completing their cardiac rehab program. However, evidence from prior aerobic exercise intervention trials with older adults have been mixed, some reporting increased CBF at rest, and others reporting no difference.

Our work demonstrates the importance of measuring dynamic response to exercise. Drs. [name] and [name] recently described the dynamic change in a measure of CBF with onset of exercise in young and older individuals (Figure 2) demonstrating that older adults have a pronounced blunting of CBF during exercise that was less evident at rest.

Increased CBF can be measured by arterial spin labeled (ASL) MRI. Optimal imaging parameters to capture CBF response to acute exercise using ASL, identifying a 20% increase immediately following an acute bout of exercise.

Drs. [name] and [name] on our team have conducted a pilot study ( $n=11$ ) to examine changes in blood flow following acute exercise (50-70% max HR) compared to quiet rest in smokers. ASL was performed  $\sim$ 30 minutes after exercise. Analyses revealed a pattern of increased CBF generally, and in ACC and precentral gyrus specifically,  $p < 0.16$ .

*This collective body of work demonstrates our ability to capture CBF change with highly coordinated, precisely timed acute exercise protocols. It also provides a compelling case for exploring the cerebrovascular exercise response in relationship to AD risk.*

[figure not shown]

Figure 1. CBF response to exercise (cm/s, the ordinate) is lower in cognitively normal individuals with greater  $\beta$ -amyloid burden (standard uptake value ratio, the abscissa). Open circles are individuals with elevated  $\beta$ -amyloid. Sisante et al. J Cereb Blood Flow Metabol 2017.

[figure not shown]

Figure 2. Middle cerebral artery velocity response at the onset of exercise (cm/s, the ordinate) is diminished in older individuals. Dashed line is onset of moderate exercise. ([name] et al. J Appl Physiol 2017.)

**Interaction of CBF, neurotrophins, and APOE Genotype:** The **scientific premise** underlying this proposal is that CBF and blood-based biomarkers such as VEGF, BDNF, and IGF1 are interrelated mechanisms driving chronic aerobic exercise effects on brain health and cognition. Several lines of evidence are now converging to point to these interacting factors as critical for supporting cognition and brain health into old age.

There are well-documented differences in cerebral blood flow (CBF) and tissue oxygenation based on age or APOE genotype, with deleterious consequences for cognition. Cerebrovascular endothelial cells respond to the shear force stress on the vessel walls by releasing BDNF. Further, carotid occlusion extinguishes exercise-induced BDNF increases in the brain, strongly suggesting that increased cerebral blood flow is a key trigger of BDNF release. Therefore, maintenance or improvement in CBF is likely an important mediator brain health and cognitive effects as we age.

Because VEGF is a salient promoter of vascularization, it is an evident candidate for association with CBF. Previous work demonstrates that rodent neuro- and angiogenesis are coupled with CBF following an exercise

intervention. However, it is unclear if APOE4 moderates this relationship. Recently it has been suggested that APOE4-driven pathologies are mediated by a VEGF-dependent pathway but more work is needed.

It is known that the ApoE protein is important for maintaining cerebrovascular integrity. Additionally, different isoforms of the ApoE protein appear to regulate expression and release of BDNF, at least in vitro. And, though we know individuals with cognitive impairment (MCI or AD) have lower serum BDNF levels and tissue pro-BDNF, large studies have failed to demonstrate a relationship between E4 carriage and circulating BDNF levels in cognitively normal individuals.

## **Approach**

We will significantly reduce participant burden and speed execution by heavily leveraging the infrastructure of the KU ADC, one of 31 NIH-designated Alzheimer's Centers of Excellence. The KU ADC follows over 400 individuals with annual evaluations as part of our Clinical Cohort. We have extensive experience in neuroimaging and exercise testing. As presented previously, this work is a natural extension of our robust research program and will enhance our ability to measure acute exercise response. We are confident in our timing and are currently conducting a study that requires blood draws before and 15min after exercise.

**Overall Study Design:** Up 90 participants will be recruited from the KU Alzheimer's Disease Center (KU ADC) and the community. For this study, participants will attend one visit at the Hoglund Brain Imaging Center on the University of Kansas Medical Center campus. Performing all activities at the single visit reduces burden on participants and allows capture of key biomarkers in temporal relationship following a rigorous, time-sensitive protocol. Inclusion and exclusion criteria are further detailed in the Human Subjects section.

**Recruitment:** E4 carriers make up approximately 33% of the Clinical Cohort. We have an estimated 90 non-demented individuals that we can approach with an E4 allele. Based on our experience, ~60% of eligible Cohort enrollees will consent to the proposed project. Additionally, [name] directs a robust Outreach & Recruitment Core which maintains a list of 7500+ individuals who have expressed interest in dementia research. We project enrollment of 1-2 individuals per week, completing by mid-Year 2.

Genotype will not be disclosed to the participant. Study staff with direct participant contact will remain blinded to genotype. Because APOE4 does not have equal penetrance in our Cohort, we will begin by approaching an E4-enriched contact list created by the KU ADC Statistics Core (2 E4 carriers:1 non-carrier). A co-investigator not in contact with PHI ([name]) will monitor enrollment for E4 carriage and request contact list adjustments as necessary to achieve haplotype balance. We will exclude individuals with an E2 allele. We will make efforts to preferentially match APOE4 genotype groups based on sex.

In some instances, potential participants who have not been characterized in the past 6 months or at all by the KU ADC through study #11132 may express interest in participating. In these instances, the participant will be invited to identify a study partner so that the PI can adjudicate cognitive performance, the QDRS. A study partner who knows the participant well will be required to answer the QDRS questions over the phone.

We will use an approved phone screening consent from the potential participant to get basic demographic and screening information and the name of a study partner who knows the potential participant well. We will then use an approved phone consent for the study partner and ask questions regarding the cognition and function of the potential participant (approximately 10 minutes) to qualify the individual for the study. Given that all participants will have already been initially prescreened through our Recruitment and Eligibility Database (#140406) we do not believe we will encounter any individuals who cannot consent for themselves.

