**Imaging Parameters:** The investigative team has extensive experience with imaging and preliminary evidence to demonstrate the necessary skill set for capturing time-dependent ASL changes due to exercise. We will employ imaging sequences most suited to capture anatomical and brain blood flow, lasting ~20 minutes before exercise and ~30 minutes after exercise.

**Cognitive Testing:** Evidence suggests that subtle, transient cognitive effects of exercise are detectable immediately following an acute exercise bout in older adults. We will employ a short battery of cognitive tests to capture exercise-related change in: executive control, episodic memory, and processing speed. The battery will last ~20 minutes, depending on participant speed.

Our primary cognitive measure will be the response time cost of incongruent stimuli on the Flanker Test. The Flanker Test is an executive function task that measures inhibitory control with a well-documented history of indexing change following exercise intervention (our long term goal), and early in AD.

**Aim 1: Characterize CBF change after exercise.** Our primary outcome of interest for Aim 1 is global CBF percent change from baseline from rest to immediately after exercise. Secondary outcomes will be absolute change in CBF (ml/100g tissue/min) and spatial coefficient of variation (an indirect measure of arterial transit time). We hypothesize that older participants have blunted exercise-induced change in CBF.

**Aim 1 Statistical Analyses:** Custom software utilizing the ASL Toolbox for SPM 12 will quantify global CBF. Our primary and secondary outcome measures are continuous, and thus we will use linear mixed models (LMM). We will include a random intercept coefficient to allow for each pre-post exercise pair to account for individual baseline differences. Age group will be modeled as a fixed effect. Other analysis techniques may be employed as they become available.

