**Sample Size:** To our knowledge, there are currently no peer-reviewed reports of genotype-based CBF differences in response to acute exercise. However, perfusion measures in genetic risk for AD (APOE e4) have been performed previously and can form the basis of a reasonable power analyses. Thus, our sample size was determined based primarily on feasibility and preliminary data. First, KU is uniquely suited to perform this study. We have had success in recruiting and characterizing individuals for imaging and exercise studies under complex protocols. Second, two prior cross-sectional estimates of the relationship of perfusion and e4 carriage have delivered similar effect sizes ( $d=1.0$ ). Given this power, we expect to be able to discern differences between sex, and between older adults with and without cognitive impairment.

**Exploratory Aim: Describe the relationship between CBF and cognitive performance after acute exercise.** Our primary outcome will be the response time on the Eriksen Flanker Task. We will explore these cognitive effects in individuals, assessing how CBF and our blood-based biomarkers relate to cognitive improvements. These data will set the stage for future work assessing who responds to habitual exercise with cognitive improvements, and through what mechanisms.

**Exploratory Aim Statistical Analyses:** We will use the same least squares regression approach as in Aim 2.

**Data Management:** Study data will be collected and managed using the Research Electronic Data Capture (REDCap) web-based, electronic data capture tools. Imaging data will be archived and backed up on a dedicated XNAT server operated by the Hoglund Brain Imaging Center. Hoglund also maintains an imaging analysis server that provides researchers access to up-to-date imaging software (e.g. SPM). The PI has over 10 years of experience with REDCap, XNAT, and imaging analysis. Both departments ensure data security by managing all data HIPAA compliant servers that have role-based access and regular backup.

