### **Protection of Human Participants**

#### **a. Human Participants Involvement and Characteristics:**

For this study, we plan to enroll up to 80 participants from our screening population (the KU ADC Clinical Cohort, and Recruitment Database), other research databases on the KUMC campus (e.g. Pioneers or FitHawks with permission) and the community. Goal enrollment is:

- 1) up to 20 individuals, age 18-65
- 3) 60, age 65-85 (approximately equal APOE4 carrier and APOE4 non-carrier)

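### Aim 1 compares non-randomised age groups with no sex term in the model, so a difference in sex mix could confound the age contrast; pre-specifying sex as a covariate is a minor, nearly free improvement

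*Combined protocol and SAP*

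**What the plan says.** The Aim 1 paragraph of the protocol states the hypothesis as an age contrast: "We hypothesize that older participants have blunted exercise-induced change in CBF". The outcome is a within-person change: "Our primary outcome of interest for Aim 1 is global CBF percent change from baseline from rest to immediately after exercise". Aim 1 Statistical Analyses specifies a linear mixed model. Its random part is described thus: "We will include a random intercept coefficient to allow for each pre-post exercise pair to account for individual baseline differences". Its fixed part is one sentence: "Age group will be modeled as a fixed effect". The paragraph ends with an open clause: "Other analysis techniques may be employed as they become available". It names no sex covariate, stratification or sensitivity analysis.

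Sex appears in two other places. Under Approach, Recruitment: "We will make efforts to preferentially match APOE4 genotype groups based on sex". Under Sample Size, after an effect size of d = 1.0 for perfusion by e4 carriage: "we expect to be able to discern differences between sex".

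The section on human participants' involvement and characteristics sets the group sizes: "up to 20 individuals, age 18-65", and 60 aged 65 to 85 with carriers and non-carriers about equal. It sets no sex target for either age group.

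**The concern.** Age group cannot be randomised, so nothing in the design makes the two age groups alike in sex. Balance can come only from recruitment or from the model. The plan uses recruitment to balance sex between genotype groups, and uses neither tool for the age groups.

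Two features of Aim 1 look protective but cover only part of the problem. The random intercept and the percent-change outcome remove a sex difference in resting CBF. They do not remove a sex difference in the response to exercise, and that response is the outcome. If such a difference exists and the groups differ in sex mix, part of it is read as an effect of age. This could create an apparent blunting in older participants or hide a real one.

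**Working it through.** **Inputs from the protocol.** Younger group: up to 20. Older group: 60. (Approach gives a total of up to 90 and the human participants section up to 80. Only the latter gives the split by age, so 20 and 60 are used.) Model: age group as the only named fixed effect.

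**The plan's own figure.** The only one is d = 1.0, for perfusion by e4 carriage. No alpha, power or derived sample size is attached, so there is nothing to reproduce, and it says nothing about sex or about CBF change.

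**Assumptions.** Sex shifts CBF change by b SD, with b from 0.5 to 1.0, because the documents give no value. Tests are two-sided at 5%. The within-sex SD of change is set to 1.

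**Step 1: how large an imbalance arises by chance.** With 50% women expected in both groups:

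SD of the difference in share of women = √(0.25/20 + 0.25/60) = √0.01667 = 0.129, or 12.9 points.

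Exact binomial results: the mean absolute difference is about 10 points. The difference is at least 15 points in 27% of trials, at least 20 in 14%, at least 25 in 6% and at least 30 in 2%.

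**Step 2: shift in the age contrast.** Shift = imbalance × b. The unadjusted standard error is √(1/20 + 1/60) = 0.258 SD.

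| Imbalance | b = 0.5 | b = 1.0 | Shift ÷ standard error |
|---|---|---|---|
| 10 points | 0.05 SD | 0.10 SD | 0.19 to 0.39 |
| 25 points | 0.125 SD | 0.25 SD | 0.48 to 0.97 |

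**Step 3: type I error of the unadjusted age test, by simulation.**

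- *Imbalance arises only by chance, with the same expected sex mix in both groups:* about 5% for b = 0.5 and for b = 1.0. The shift averages zero over trials, and the ordinary standard error already contains it.
- *Imbalance held at 20 points (8/20 vs 36/60):* 5.8% for b = 0.5 and 7.6% for b = 1.0.
- *Imbalance held at 30 points (7/20 vs 39/60):* 7.6% and 15.5%.
- *Systematic difference, source populations 70% vs 50% women, b = 1.0:* about 11%. The mean shift is 0.20 × 1.0 = 0.20 SD.

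**Step 4: the same test with sex in the model.** The shift is zero and the type I error about 5% in every scenario. The standard error rises from 0.258 to 0.262 SD at a 20-point imbalance, to 0.268 at 30 points and to 0.276 at 40 points. At 30 points that is 0.268/0.258 = 1.04, an increase of about 4%.

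**The case against.** The strongest reply is that chance imbalance is not bias. If both age groups have the same expected sex mix, the unadjusted test keeps its 5% level, and the average shift of 0.05 to 0.10 SD is small against a standard error of 0.258 SD. This stands. The higher error rates in Step 3 require a given imbalance or a systematic difference in sex mix, and mostly a large sex effect as well. What remains is that adjustment also protects the estimate in the particular sample obtained, and that the documents do not rule out a systematic difference.

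A reader might infer four stronger points that the documents do not support.

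- *The younger group comes from different sources, so its sex mix will differ.* The human participants section lists the clinical cohort, recruitment database, campus databases and community for the whole sample, and assigns none to an age group. Different sourcing is possible but not stated.
- *The plan predicts a sex difference.* The sentence "we expect to be able to discern differences between sex" is a claim about power. It does not say that the CBF response to exercise differs by sex.
- *A sizeable imbalance is likely.* At least 15 points occurs in 27% of trials and at least 25 points in 6%. That is a risk, but not the likely outcome.
- *Sex matching is spent on a contrast that no aim tests.* The Exploratory Aim's analysis refers to an Aim 2 that is not set out in the text, so this cannot be established. Matching genotype groups on sex fits the APOE4 rationale of the background and sample-size sections.

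It could also be said that the open clause on other techniques permits adjustment. It does, but it does not pre-specify it. A covariate chosen after the data are seen is less credible.

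**Conclusion.** The point holds as a minor one. The Aim 1 model has no sex term, and the age groups are neither randomised nor matched on sex. The age contrast is therefore confounded if two conditions hold together: the groups differ in sex mix, and sex affects the exercise response. The documents establish neither condition and exclude neither.

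Its size rests on the assumed sex effect of 0.5 to 1.0 SD. The shift is 0.05 to 0.10 SD at a typical chance imbalance, and 0.13 to 0.25 SD at an imbalance seen by chance in about 6% of trials. It scales in proportion for a smaller or larger sex effect. The working does not show that the planned test is invalid: its level is lost only under a systematic difference in sex mix. The case for change is that the remedy costs almost nothing.

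**What to change.** In Aim 1 Statistical Analyses, name sex as a pre-specified fixed effect. If the mixed model is fitted to the pre- and post-exercise values, include sex-by-time alongside the age-by-time term that carries the hypothesis, because a main effect of sex alone adjusts the level of CBF and not its change. If percent change is analysed as a single value per person, enter sex as a covariate.

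The cost is a sentence in the plan, about one degree of freedom for the age contrast, and a rise in its standard error from 0.258 to at most 0.268 SD for imbalances up to 30 points. No new data are needed, since the plan to match on sex presupposes that it is recorded.

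Extending the best-effort sex matching to the younger group is optional. It adds little once sex is in the model, and may slow the filling of the last younger places slightly.
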